5.7 Criteria for Taking a Participant Off Study

Participants will be removed from study when any of the following criteria apply:

- Completion of all study-related activities
- Lost to follow-up
- Withdrawal of consent
- Death

The reason for taking a participant off study, and the date the participant was removed, must be documented in the case report form (CRF).

For Centralized Subject Registrations, the research team submits a completed Off Treatment/Off Study form to ODQ when a participant comes off study. This form can be found on the ODQ website or obtained from the ODQ registration staff.

For Decentralized Subject Registrations, the research team updates the relevant Off Treatment/Off Study information in OnCore.

5.8 Treatment Past Disease Progression

It is now increasingly recognized that patterns of response may differ with immunotherapeutic anti-cancer agents, compared with patterns seen with conventional cytotoxic agents. In particular, in patients receiving checkpoint blockade therapy for solid tumors, the phenomenon of immune flare or pseudo-progression has been described; patients who experience pseudo-progression can still derive significant benefit from treatment. This has led to a modification of response criteria (the LyRIC criteria) for patients with lymphoma treated with immunotherapy (32). The management of patients with apparent progressive disease on this trial should generally follow the recommendations of the LyRIC criteria. Patients with confirmed PD using LyRIC criteria who are still felt to derive clinical benefit and have no alternative option for care may still continue on therapy past PD, after consultation with the study chair.

Criteria for treatment beyond PD (in addition to discussion with study chair):

- Absence of signs or symptoms of progressive disease, including laboratory abnormalities
- No decrease in ECOG performance status
- Absence of rapid PD
- Absence of PD at an anatomically critical site

6. DOSING DELAYS/DOSE MODIFICATIONS

There will be no dose modifications on this study. Dose delays will be made as indicated in the following table(s). The descriptions and grading scales found in the revised NCI Common Terminology Criteria for Adverse Events (CTCAE) version 4.0 will be utilized for dose delays and dose modifications. A copy of the CTCAE version 4.0 can be downloaded from the CTEP website:

http://ctep.cancer.gov/protocolDevelopment/electronic_applications/ctc.htm

If a participant is delayed but is subsequently able to resume treatment, then subsequent visits, assessments and treatments will continue every 3 weeks (unless the dosing interval is modified per Table 2) **from the time treatment has resumed until all cycles of therapy are completed.** For example, if cycle 4 is delayed 2 weeks and administered on week 12 instead of 10, cycle 5 and its corresponding assessments should take place on week 15, cycle 6 on week 18, etc.

Pembrolizumab will be withheld for drug-related Grade 4 hematologic toxicities, non-hematological toxicity \geq Grade 2 or 3 (depending on nature of toxicity) including laboratory abnormalities, and severe or life-threatening AEs as per Tables 2 and 3 below. If there is a question as to whether an AE is or is not immune-related, this should be discussed with the study chair.

Table 2. Dose Modification Guidelines for Hematological Drug-Related Adverse Events.

Toxicity	Grade	Hold treatment	Timing for restarting treatment	Treatment discontinuation
Hematological	1,2,3	No	N/a	N/a
	4	Yes	Toxicity resolves to grade ≤ 1	Toxicity does not resolve within 12 weeks of last infusion Permanent discontinuation should be considered for any life-threatening event

Adverse events (both non-serious and serious) associated with pembrolizumab exposure may represent an immunologic etiology. These adverse events may occur shortly after the first dose or several months after the last dose of treatment. Pembrolizumab must be withheld for drug-related toxicities and severe or life-threatening AEs as per Table 3 below.

Table 3. Dose modification guidelines for non-hematological drug related adverse events including immune related adverse events (irAEs)

General instructions:				
Immune-related AEs	Toxicity grade or conditions (CTCAEv4.0)	Action taken to pembrolizumab	irAE management with corticosteroid and/or other therapies	Monitor and follow-up
Pneumonitis	Grade 2	Withhold	
 Administer corticosteroids (initial dose of 1-2 mg/kg prednisone or equivalent) followed by taper 	
 Monitor participants for signs and symptoms of pneumonitis Evaluate participants with suspected pneumonitis with radiographic imaging and initiate corticosteroid treatment Add prophylactic antibiotics for opportunistic infections
	Grade 3 or 4, or recurrent Grade 2	Permanently discontinue		
Diarrhea / Colitis	Grade 2 or 3	Withhold	
 Administer corticosteroids (initial dose of 1-2 mg/kg prednisone or equivalent) followed by taper 	
 Monitor participants for signs and symptoms of enterocolitis (ie, diarrhea, abdominal pain, blood or mucus in stool with or without fever) and of bowel perforation (ie, peritoneal signs and ileus). Participants with \geq Grade 2 diarrhea suspecting colitis should consider GI consultation and performing endoscopy to rule out colitis. Participants with diarrhea/colitis should be advised to drink liberal quantities of clear fluids. If sufficient oral fluid intake is not feasible, fluid and electrolytes should be substituted via IV infusion.
	Grade 4	Permanently discontinue		
AST / ALT elevation or Increased	Grade 2	Withhold	
 Administer corticosteroids (initial dose of 0.5- 1 mg/kg prednisone or equivalent) followed by taper 	
 Monitor with liver function tests (consider weekly or more frequently until liver enzyme value returned to baseline or is

bilirubin	Grade 3 or 4	Permanently discontinue	
 Administer corticosteroids (initial dose of 1-2 mg/kg prednisone or equivalent) followed by taper 	stable
Type 1 diabetes mellitus (T1DM) or Hyperglycemia	Newly onset T1DM or Grade 3 or 4 hyperglycemia associated with evidence of β -cell failure	Withhold	
 Initiate insulin replacement therapy for participants with T1DM Administer anti-hyperglycemic in participants with hyperglycemia 	
 Monitor participants for hyperglycemia or other signs and symptoms of diabetes.
Hypophysitis	Grade 2	Withhold	
 Administer corticosteroids and initiate hormonal replacements as clinically indicated. 	
 Monitor for signs and symptoms of hypophysitis (including hypopituitarism and adrenal insufficiency)
	Grade 3 or 4	Withhold or permanently discontinue ¹		
Hyperthyroidism	Grade 2	Continue	
 Treat with non-selective beta-blockers (eg, propranolol) or thionamides as appropriate 	
 Monitor for signs and symptoms of thyroid disorders.
	Grade 3 or 4	Withhold or permanently discontinue ¹		
Hypothyroidism	Grade 2-4	Continue	
 Initiate thyroid replacement hormones (eg, levothyroxine or liothyroinine) per standard of care 	
 Monitor for signs and symptoms of thyroid disorders.
Nephritis and Renal dysfunction	Grade 2	Withhold	
 Administer corticosteroids (prednisone 1-2 mg/kg or equivalent) followed by taper. 	
 Monitor changes of renal function
	Grade 3 or 4	Permanently discontinue		
Myocarditis	Grade 1 or 2	Withhold	
 Based on severity of AE administer corticosteroids 	
 Ensure adequate evaluation to confirm etiology and/or exclude other causes
	Grade 3 or 4	Permanently discontinue		
All other immune-related AEs	Intolerable/ persistent Grade 2	Withhold	
 Based on type and severity of AE administer corticosteroids 	
 Ensure adequate evaluation to confirm etiology and/or exclude other causes
	Grade 3	Withhold or discontinue based on the type of		

		event. Events that require discontinuation include and not limited to: Gullain-Barre Syndrome, encephalitis		
	Grade 4 or recurrent Grade 3	Permanently discontinue		

1. Withhold or permanently discontinue pembrolizumab is at the discretion of the investigator or treating physician.

NOTE:
For participants with Grade 3 or 4 immune-related endocrinopathy where withhold of pembrolizumab is required, pembrolizumab may be resumed when AE resolves to \leq Grade 2 and is controlled with hormonal replacement therapy or achieved metabolic control (in case of T1DM).

Dosing interruptions are permitted in the case of medical / surgical events or logistical reasons not related to study therapy (e.g., elective surgery, unrelated medical events, patient vacation, and/or holidays). Subjects should be placed back on study therapy within 3 weeks of the scheduled interruption, unless otherwise discussed with the principal investigator. The reason for interruption should be documented in the patient's study record.

Management of suspected immune related AEs should follow the guidelines provided in section 5.4.2.

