d:	In subjects who discontinue therapy without documented disease progression every effort should be made to continue monitoring disease by radiographic imaging every 12 weeks (\pm 14 days) until one of the following occurs: start of new anti-cancer therapy; documented disease progression by investigator assessment; end of study; or death, whichever occurs first												
e:	After the start of new anti-cancer treatment or documented disease progression by investigator assessment, the subject will transition to the Survival Follow-up and the patient or their primary physician should be contacted by telephone or email every 12 weeks (+/- 14 days) to assess survival status												
f:	Patients who achieve a metabolic complete remission (defined as Deauville 1-3) may be followed subsequently with CT of the chest, abdomen, and pelvis rather than PET/CT at the discretion of the treating investigator; after cycle 9 radiology restaging will occur every 4 cycles (e.g. on cycles 13, 17, 21, etc) until cycle 33. There is a \pm 3-day window for radiology tests but radiographic restaging should occur prior to drug administration for a cycle on which restaging is due though this could include a scan the same day as but prior to dosing of study drug.												
g:	At screening, fresh biopsy (1 core) or archival tissue within 90 days of C1D1 (5 unstained slides, 5 μ m) is required, unless an exception is given by the study chair. Fresh biopsy samples at week 6 (\pm 7 days) and at the time of discontinuation due to disease progression are optional but highly recommended unless the tumors are considered inaccessible by the treating physician or concerns that a biopsy is contraindicated due to safety concerns.												
h:	In subjects with an unconfirmed PD assessment who continue study therapy a radiology assessment should be performed 12 weeks (\pm 7 days) from the time of unconfirmed PD assessment or at the time of treatment discontinuation. If a scan was previously obtained within 30 days of the time of treatment discontinuation then a repeat radiology examination is not required. Imaging should occur at any time that disease progression is suspected. Those who have EBV positive lymphoma will have EBV viral load assessed at screening. If positive, it will be subsequently checked at every disease assessment.												

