11. MEASUREMENT OF EFFECT

11.1 Response Criteria

The primary objective of this study is overall response rate (ORR). Response and progression will be evaluated following the 2014 Lugano criteria for the primary endpoint and LyRIC for secondary endpoint. Patients will undergo tumor restaging, using the appropriate combination of imaging and bone marrow biopsies, after cycles 2 and 5 and 8 and then every 4 cycles thereafter until cycle 32. Radiographic restaging will also be performed at the 60-day post-treatment follow-up visit and at pre-specified intervals thereafter (see Study Calendar, section 10). Imaging will consist of PET/CT scans until the patient has achieved a metabolic CR (defined as Deauville score 1-3) at which juncture transition to CT of the chest, abdomen and pelvis will be acceptable at the discretion of the treating physician. Response assessment will follow standard criteria (Lugano criteria) for lymphoma. Bone marrow biopsy will be required within 30 days of radiology testing to confirm CR for patients with marrow involvement at baseline. A repeat bone marrow biopsy is not necessary to confirm CR if there was no marrow involvement at baseline.

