APPENDIX B

LUGANO AND LYRIC RESPONSE CRITERIA (31, 32)

Criteria	CR	PR	PD
Lugano	PET-CT, score 1, 2, or 3* with or without a residual mass on 5PS [†] OR on CT, target nodes/nodal masses must regress to ≤ 1.5 cm in LDi	PET-CT score 4 or 5 with reduced uptake compared with baseline and residual mass(es) of any size. OR On CT $\geq 50\%$ decrease in SPD of up to 6 target measurable nodes and extranodal sites	
PET-CT score 4 or 5 with an increase in intensity of uptake from baseline and/or new FDG-avid foci consistent with lymphoma at interim or end-of-treatment assessment. OR On CT, an individual node/lesion must be abnormal with: LDi > 1.5 cm and increase by $\geq 50\%$ from PPD nadir and an increase in LDi or SDi from nadir 0.5 cm for lesions ≤ 2 cm 1.0 cm for lesions > 2 cm
 
In the setting of splenomegaly, the splenic length must increase by $> 50\%$ of the extent of its prior increase beyond baseline (eg, a 15-cm spleen must increase to > 16 cm). If no prior splenomegaly, must increase by ≥ 2 cm from baseline. New or recurrent splenomegaly
 
New or clear progression of preexisting nonmeasured lesions
 
Regrowth of previously resolved lesions
 
A new node > 1.5 cm in any axis or a new extranodal site > 1.0 cm in any axis; if < 1.0 cm in any axis, its presence must be unequivocal and must be attributable to lymphoma
 
Assessable disease of any size unequivocally attributable to lymphoma
 
AND/OR new or recurrent involvement of the bone marrow
 
As with Lugano with the following exceptions:

LYRIC	Same as Lugano	Same as Lugano	
IR
 
IR(1): $\geq 50\%$ increase in SPD in first 12 weeks
 
IR(2): $< 50\%$ increase in SPD with
 
a. New lesion(s), or
 
b. $\geq 50\%$ increase in PPD of a lesion or set of lesions at any time during treatment
 
IR(3): Increase in FDG uptake without a concomitant increase in lesion size meeting criteria for PD

- IR, immune response; LDi, longest diameter; PPD, product of the perpendicular diameters; SDi, short diameter; 5PS, 5-point scale.
- d* A score of 3 in many patients indicates a good prognosis with standard treatment, especially if at the time of an interim scan. However, in trials involving PET where de-escalation is investigated, it may be preferable to consider a score of 3 as inadequate response (to avoid undertreatment).

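### On-treatment restaging follows the dosing cycle, so a drug hold also delays the next scheduled scan; the effect on PFS, duration of response and LyRIC IR(1) is modest and cheap to remove

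*Combined protocol and SAP*

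**What the plan says.** Section 6 says that after a delay "subsequent visits, assessments and treatments will continue every 3 weeks", and that this runs "from the time treatment has resumed until all cycles of therapy are completed". The anchor is the resumed dose, not C1D1.

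Section 11.1 places restaging "after cycles 2 and 5 and 8 and then every 4 cycles thereafter until cycle 32". Section 10, footnote f, adds that "radiographic restaging should occur prior to drug administration for a cycle on which restaging is due", with a window of 3 days either side. Scans therefore precede cycles 3, 6, 9, 13, 17 and so on. Section 5.1 lets a cycle run longer than 21 days for an adverse effect, so the end of a cycle moves with a hold.

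Calendar-time imaging appears in only two places: every 12 weeks after therapy stops without progression (Section 10, footnote d), and 12 weeks after an unconfirmed progression (footnote h). Footnote h also asks for imaging whenever progression is suspected.

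For drug-related grade 4 hematologic events, Table 2 ends treatment if "Toxicity does not resolve within 12 weeks of last infusion". Section 6 normally limits interruptions unrelated to therapy to 3 weeks. Section 11.2.1 ends duration of response when progression is objectively documented, and Section 11.2.2 has no rule for late scans in PFS. In Appendix B, IR(1) requires the "increase in SPD in first 12 weeks".

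**The concern.** The time at which disease is looked at should not depend on whether drug was given on time. Here it does: a patient on hold has no scheduled scan until dosing resumes, whereas a patient permanently off drug without progression has a calendar schedule. Progression that arises silently during a hold is recorded at a later date than it would have been on the planned grid.

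At stake are the dates behind PFS and duration of response, and one LyRIC category. If the first scan falls after week 12, the same growth that could have been IR(1) on schedule can no longer be so classified, purely because of dosing history. LyRIC outcomes are secondary endpoints, and Section 5.8 uses LyRIC to guide the handling of apparent progression.

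**Working it through.** **The plan's own example.** With C1 in week 1, cycle k falls in week 1 + 3(k − 1) + cumulative hold. Section 6 supposes a case in which "if cycle 4 is delayed 2 weeks and administered on week 12 instead of 10": 10 + 2 = 12, which agrees. It then says "cycle 5 and its corresponding assessments should take place on week 15": 12 + 3 = 15, which agrees. C6 falls in week 18, as stated. C6 is a restaging cycle, so its scan moves from week 16 to week 18.

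**Scheduled scans without holds.** Weeks after C1D1 = 3(k − 1): C3 at 6, C6 at 15, C9 at 24, C13 at 36, then every 12 weeks.

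**First scan with a hold of h weeks before C3.** Time = 6 + h.

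- h = 2, 4, 6, 7, 9 gives weeks 8, 10, 12, 13, 15. The 12-week window is missed once h exceeds 6.
- One hold at the Table 2 limit is 12 − 3 = 9 weeks beyond the due dose, giving week 15.
- One 3-week interruption unrelated to therapy gives week 9; two give week 12, still not beyond the window.
- The same 9-week hold stretches a later gap from 9 to 18 weeks, or from 12 to 21 weeks after C9.

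**Effect on documented PFS.** Assumptions, none from the documents: exponential latent progression with median m weeks, progression found only at scheduled scans, no deaths, and 20% of patients held 9 weeks before the first scan. The held grid is 15, 24, 33, 45...; the planned grid is 6, 15, 24, 36...

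*At 12 weeks.* On schedule, documented PFS = 2^(−6/m). No held patient has been scanned, so the mixture is 0.8 × 2^(−6/m) + 0.2.

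*Mean.* Let M be the mean documented time on schedule: M = 6 + 9·2^(−6/m) + 9·2^(−15/m) + 12·2^(−24/m)/(1 − 2^(−12/m)), with 12-weekly scans continued indefinitely. A hold of h before scan 1 adds h − (1 − 2^(−h/m))(M − 6) per held patient; multiplying by 0.2 spreads this over all patients.

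| m (weeks) | 12-week PFS, planned → with holds | M | Extra per held patient, h = 9 | Extra over all patients | Extra per held patient, h = 4 |
|---|---|---|---|---|---|
| 9 | 63.0% → 70.4% | 17.64 | 9 − 0.500 × 11.64 = 3.2 | 0.6 | 0.9 |
| 13 | 72.6% → 78.1% | 23.64 | 9 − 0.381 × 17.64 = 2.3 | 0.5 | 0.6 |
| 26 | 85.2% → 88.2% | 42.82 | 9 − 0.213 × 36.82 = 1.1 | 0.2 | 0.3 |

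*At 26 weeks.* Both grids have their last scan at week 24, so documented PFS is 2^(−24/m) either way: no change.

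*Median.* For m = 9 and 13, documented PFS first falls below 50% at week 15 (31.5% and 44.9%) in both cases, because both grids have a scan then. For m = 26 it is week 36 in both cases. At week 33 the mixture is 0.8 × 52.7% + 0.2 × 41.5% = 50.5%, still above 50% and below the 52.7% of the planned grid. A shifted grid therefore also catches some progressions earlier.

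**The case against.** Several points on the other side stand.

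- *A hold at C3 need not delay the C3 scan.* The scan is already due at that visit, and Section 6 moves only subsequent assessments. The delay is clear for a hold at C2; at C3 it arises only if the due scan has not yet been done.
- *The 9-week figure is extreme.* The 12-week limit applies to grade 4 hematologic events, and Section 7.1 lists thrombocytopenia as occasional and other cytopenias as rare. Nothing in the documents supports 20% of patients being held that long.
- *For-cause imaging is a real safeguard.* A reader might infer that footnote h catches symptomatic progression only. It has no such restriction; examination, laboratory results or EBV load could raise suspicion. Leaving such scans out makes the calculation an upper bound.
- *Duration of response is not always overstated.* A hold before first response also delays its start date.
- *Cycle-based scans have a rationale.* They measure response after a set number of doses, which is coherent when ORR is primary.

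A reader might also infer that immune-related holds are unlimited, because no limit is visible in Table 3. Its general-instructions row is empty in the text available, so that inference is unsafe and is not used here.

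None of this removes the mechanism: no provision keeps scheduled scans on time during a hold.

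**Conclusion.** The point holds in a limited form. A hold that starts before a restaging cycle delays the next scheduled scan by its own length, progression not otherwise suspected is then dated late, and a cumulative hold of more than 6 weeks before C3 loses the IR(1) window. IR(2) and IR(3) are unaffected, and a 2- to 4-week hold does not cause the loss.

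Under the assumptions above, 12-week documented PFS rises by about 3 to 7 percentage points, while the overall mean moves by less than a week. With a more ordinary 4-week hold, the mean delay among held patients is 0.3 to 0.9 weeks.

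A reader might conclude that the trial's PFS is materially inflated or its main result compromised. The documents do not support that. The rule of at least 6 responders among 20 patients, and its power for 15% against 40%, are unchanged. PFS and duration of response are descriptive single-arm estimates, with no planned comparison of held and unheld patients. This is a worthwhile, inexpensive improvement, not a flaw that threatens the trial's conclusion.

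**What to change.** In Section 6, exclude disease assessments from the shift that follows a delayed dose. In Section 11.1 and Section 10, footnote f, set restaging at 6, 15 and 24 weeks from C1D1 and every 12 weeks thereafter, whether or not drug is held, until progression or new anti-cancer therapy. Leave the dosing rules and for-cause imaging as they are. This keeps the planned intervals and extends the calendar approach of footnote d to patients temporarily off drug.

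The cost is amendment wording in three sections. After a delay, scans may not coincide with dosing visits, and a held patient may be scanned after fewer doses than planned. A long hold may also bring one more on-treatment scan: C35 falls 3 × 34 = 102 weeks after C1D1, so a 9-week hold moves it to week 111, past a scan at week 96 + 12 = 108.

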7. ADVERSE EVENTS: LIST AND REPORTING REQUIREMENTS

An adverse event is defined as any untoward medical occurrence in a patient or clinical investigation subject administered a pharmaceutical product and which does not necessarily have to have a causal relationship with this treatment. An adverse event can therefore be any unfavorable and unintended sign (including an abnormal laboratory finding, for example), symptom, or disease temporally associated with the use of a medicinal product or protocol-specified procedure, whether or not considered related to the medicinal product or protocol-specified procedure. Any worsening (i.e., any clinically significant adverse change in frequency and/or intensity) of a preexisting condition that is temporally associated with the use of the pembrolizumab, is also an adverse event.

Changes resulting from normal growth and development that do not vary significantly in frequency or severity from expected levels are not to be considered adverse events. An example of this may include, but is not limited to, menopause occurring at a physiologically appropriate time.

Adverse events may occur during the use of pembrolizumab in clinical trials, or as prescribed in clinical practice, from overdose (whether accidental or intentional), from abuse and from withdrawal.

Progression of the cancer under study is not considered an adverse event.

All adverse events that occur after the consent form is signed but before treatment allocation/randomization must be reported by the investigator if they cause the subject to be excluded from the trial, or are the result of a protocol-specified intervention, including but not limited to washout or discontinuation of usual therapy, diet, placebo treatment or a procedure.

From the time of treatment allocation/randomization through 30 days following cessation of treatment, all adverse events must be reported by the investigator. Such events will be recorded at each examination on the Adverse Event case report forms/worksheets. The reporting timeframe for adverse events meeting any serious criteria is described in Section 7.2. The investigator will make every attempt to follow all subjects with non-serious adverse events for outcome.

Adverse events will not be collected for subjects during the pre-screening period (for determination of archival tissue status) if that subject has not undergone any protocol-specified

procedure or intervention. If the subject requires a blood draw, fresh tumor biopsy etc., the subject is first required to provide consent to the main study and AEs will be captured per guidelines for standard AE reporting. The following list of reported and/or potential AEs (Section 7.1) and the characteristics of an observed AE (Section 7.2) will determine whether the event requires expedited reporting **in addition** to routine reporting.

